Abbreviations: ADA = anti-drug antibody; AE = adverse event; aPTT = activated partial thromboplastin time; BMS = Bristol Myers Squibb; C = cycle; CRPC = castration-resistant prostate cancer; CT = computed tomography; CXDY = Cycle X Day Y, as an example; D = day; DNA = deoxyribonucleic acid; ECG = electrocardiogram; ECOG = Eastern Cooperative Oncology Group; EORTC QLQ-C30 = European Organisation for Research and Treatment of Cancer Quality of Life Questionnaire – Core 30; EOT = end of treatment; EQ-5D-3L = European Quality of Life – 5 Dimension – 3 Level Questionnaire; FACIT GP5 = Functional Assessment of Chronic Illness Therapy General Physical item 5; HBV = hepatitis B virus; HCC = hepatocellular carcinoma; hCG = human chorionic gonadotropin; HCV = hepatitis C virus; INR = international normalized ratio; MRI = magnetic resonance imaging; PCWG3 = Prostate Cancer Working Group 3; PD-L1 = programmed death ligand-1; PE = physical examination; PK = pharmacokinetic; PRO-CTCAE = Patient-Reported Outcomes version of the Common Terminology Criteria for Adverse Events; PSA = prostate-specific antigen; PT = prothrombin time; Q4W = every 4 weeks; Q8W = every 8 weeks; Q12W = every 12 weeks; RECIST = Response Evaluation Criteria in Solid Tumors; RNA = ribonucleic acid; SAE = serious adverse event; SARS-CoV-2 = severe acute respiratory syndrome coronavirus 2; TNBC = triple-negative breast cancer; WOCBP = women of childbearing potential.

Protocol Amendment No.: 09

^a EOT is defined as the visit where the decision is made to discontinue the participant from treatment. Evaluations will be performed prior to study discharge, or for participants who are prematurely discontinued.

For participants who complete all scheduled cycles of therapy, the EOT visit will be the same as the last scheduled and completed on-treatment visit (eg, C26D1) and the start of the Safety Follow-up Period. For participants who do not complete all scheduled cycles of therapy, the EOT visit will be the most recent on-treatment visit (with all available safety and response data); it does not need to be repeated and will be considered as the start of the Safety Follow-up Period.

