^a Follow-up visits at Days 30 (±7 days), 60 (±7 days), and 100 (±7 days) should occur relative to the last dose of study treatment or date of discontinuation, whichever is later.

b Participants will be followed for all SAEs, non-serious AEs of special interest (as defined in Section 9.2), and all AEs (SAEs and non-serious AEs) associated with confirmed or suspected SARS-CoV-2 infection until resolution, the condition stabilizes, the event is otherwise explained, the event is deemed irreversible, the participant is lost to follow-up (as defined in Section 8.3), or for suspected cases, until SARS-CoV-2 infection is ruled out.

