Variable: Treatment Related AE with CTCAE Grade 3 or higher that occurred within 24 weeks from first dose Intercurrent events: early discontinuation of study

Treatment Policy: Patients that discontinue treatment early will have a 100 days post last dose safety follow-up. AEs occurring after this safety follow-up window will not be included in the analysis, even if they occurred within the 24 weeks from first dose.

Intercurrent event: initiation of subsequent anti-cancer therapy

While on treatment: Patients that initiate an anti-cancer subsequent therapy will be discontinued from study but will be followed up for safety events 100 days from last dose. Safety events regardless of whether they occur before or after subsequent therapy will be include in the analysis. AEs occurring past 100 days safety follow-up will not be included in the analysis, even if they occurred within the 24 weeks from first dose.

Intercurrent event: death and withdrew

While on treatment: Patients who die or withdraw consent before reaching the 24 weeks landmark will be included in the analysis and their Grade 3 to 5 treatment related AEs will be include in the summary.

Population level summary: Grade 3 to 5 treatment related adverse event incidence rate, comparison of Arm C vs Arm D and Arm F vs Arm D with estimated difference and odd ratio and 80% confidence interval using Cochran Mantel Haenszel methodology adjusting for stratification factors will be computed. Adjusted and unadjusted chi square test will be performed and p-values will be provided.

Objective	Endpoint
Primary	Primary
To evaluate the preliminary efficacy of BMS-986249 in combination with nivolumab (Arm C and Arm F) relative to historic nivolumab monotherapy data in participants with previously untreated, unresectable or metastatic melanoma	ORR as assessed by investigator using RECIST v1.1

Main Estimand for the Primary Objective

Treatment: 1200 mg BMS-986249 IV Q8W + 480 mg nivolumab IV Q4W (Arm C); 3 mg/kg ipilimumab Q3W + 1 mg/kg nivolumab IV Q3W for 4 doses followed three weeks later by 480 mg nivolumab IV Q4W(Arm D); 600 mg BMS-986249 IV Q4W + 480 mg nivolumab IV Q4W (Arm F)

Population: All treated participants with evaluable baseline tumor assessment per RECIST v1.1

Variable: BOR, defined as the best response, as determined by investigator, per RECIST 1.1

Intercurrent events: early discontinuation of study

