5.1.5 Follow-up

5.1.5.1 Safety Follow-up Period

Upon completion of study therapy (or up to a maximum of 2 years, if applicable) or once the decision is made to discontinue the participant from treatment, that is, at end of treatment (EOT), all participants will enter a Safety Follow-up Period.

For participants who will complete all scheduled cycles of therapy, the EOT visit will be the same visit as the last scheduled and completed on-treatment visit and will be the start of the Safety Follow-up Period. For participants who will not complete all scheduled cycles of therapy, the EOT visit will be the most recent on-treatment visit (with all available safety and response data) and will not need to be repeated. Accordingly, for these participants, this visit will be considered the start of the Safety Follow-up Period.

After the EOT visit, follow-up study visits should occur at Days 30, 60, and 100 (±7 days) for all study participants. Safety reporting of AEs and SAEs should take place from date of informed consent through 100 days post EOT.

All participants should complete the 3 clinical safety follow-up visits regardless of whether new anti-cancer therapy is started, except those participants who withdraw consent for study participation.

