8 DISCONTINUATION CRITERIA

8.1 Discontinuation from Study Treatment

Participants MUST discontinue IP for any of the following reasons:

- Documented disease progression as defined by RECIST v1.1 (Appendix 5) or PCWG3 (Appendix 6) unless participants meet criteria for treatment beyond progression (Section 8.1.1).
- Clinical deterioration while receiving active study therapy that, in the opinion of the investigator, indicates that continued participation in the study is not in the best interest of the participant.
- Any drug-related AE occurring at any time that meets DLT criteria as outlined in Section 7.5.1 will require permanent discontinuation. Exceptions to permanent discontinuation are listed in Section 7.5.4.
- Participant's request to stop study treatment. Participants who request to discontinue study treatment will remain in the study and must continue to be followed for protocol-specified

- follow-up procedures. The only exception to this is when a participant specifically withdraws consent for any further contact with him/her or persons previously authorized by participant to provide this information.
- Any clinical AE, laboratory abnormality or intercurrent illness which, in the opinion of the
 investigator, indicates that continued participation in the study is not in the best interest of the
 participant.
- Termination of the study by the Sponsor.
- Loss of ability to freely provide consent through imprisonment or involuntarily incarceration for treatment of either a psychiatric or physical (eg, infectious disease) illness. (Note: Under specific circumstances and only in countries where local regulations permit, a participant who has been imprisoned may be permitted to continue as a participant. Strict conditions apply and BMS approval is required).
- Inability to comply with protocol.
- Discretion of the investigator.
- Pregnancy.
- Individual participants with confirmed CR will be given the option to discontinue study therapy on a case by case basis after specific consultation and agreement between the investigator and Medical Monitor (or designee) in settings where benefit/risk justifies discontinuation of study therapy.
- Any event that leads to delay in dosing lasting > 8 weeks from the previous dose requires discontinuation, with the following exceptions:
 - Dosing delays for prolonged steroid tapers to manage drug-related AEs are allowed.

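### The 100-day safety window has three different start dates, so a few related Grade 3-5 AEs with onset before Week 24 can be collected yet left out of the primary safety endpoint

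*Combined protocol and SAP*

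**What the plan says.** Three parts of the combined document use a 100-day safety window, and each starts it from a different date.

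- **Primary estimand (Table 4-4, Part 2A; repeated in Table 4-5, Part 2B).** The variable is "Treatment Related AE with CTCAE Grade 3 or higher that occurred within 24 weeks from first dose". For early discontinuation, "Patients that discontinue treatment early will have a 100 days post last dose safety follow-up", and then "AEs occurring after this safety follow-up window will not be included in the analysis, even if they occurred within the 24 weeks from first dose". The same cut applies to participants who start another anti-cancer therapy: they "will be discontinued from study but will be followed up for safety events 100 days from last dose".
- **AE and SAE collection (Section 5.1.5.1; likewise Section 9.2.1).** "Safety reporting of AEs and SAEs should take place from date of informed consent through 100 days post EOT".
- **Follow-up visits at Days 30, 60 and 100 (Table 2-5, footnote a).** They "should occur relative to the last dose of study treatment or date of discontinuation, whichever is later".

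EOT is itself described in two ways. The schedule footnotes say "EOT is defined as the visit where the decision is made to discontinue the participant from treatment". For participants who do not complete all cycles, they and Section 5.1.5.1 also say that the EOT visit is the most recent on-treatment visit.

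The rule for early discontinuation is labelled treatment policy. In the ORR estimand of the same table, that label means that assessments count whether or not the participant is still on treatment.

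**The concern.** Last dose is never later than the other two start dates, so the estimand has the earliest close. The dates separate whenever dosing is held before treatment is stopped, which is ordinary conduct here. Section 7.5.3 requires dosing to be withheld for a range of AEs. Section 8.1 requires discontinuation only once a delay exceeds 8 weeks from the previous dose, and even then "Dosing delays for prolonged steroid tapers to manage drug-related AEs are allowed".

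In that gap the trial can collect a related Grade 3-5 event, with onset inside 24 weeks, that the primary analysis does not count. The endpoint is named as a 24-week incidence, but some early stoppers are not counted to Week 24 even where the data are in hand. A strategy label that normally means counting regardless of stopping is attached to a rule that excludes events because of time since the last dose.

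**Working it through.** **Convention.** First dose is Day 1 and 24 weeks ends on Day 168. Counting from Day 0 shifts the results by one day.

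**The plan's own figure.** Section 10.1.2.2 gives 60 per arm and about 70% power at one-sided 0.10. The assumed rates are not shown in the public text, so this cannot be reproduced exactly. The point does not depend on it.

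**Step 1: when the estimand closes before Week 24.** Close = last-dose day + 100. This is before Day 168 only if the last dose is before Day 68. Total truncation = 168 − close.

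| Arm | Last dose (day) | Close (day) | Days truncated |
|---|---|---|---|
| D (Q3W × 4) | 1 / 22 / 43 / 64 | 101 / 122 / 143 / 164 | 67 / 46 / 25 / 4 |
| C, F (nivolumab Q4W) | 1 / 29 / 57 | 101 / 129 / 157 | 67 / 39 / 11 |

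A last dose on Day 85 closes on Day 185, so nothing is truncated.

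**Step 2: how much of that is due to the mismatch.** Days collected but excluded = the smaller of (gap from last dose to EOT or discontinuation) and (days truncated). With a gap of 21 days this is 21/21/21/4 in Arm D and 21/21/11 in Arms C and F. With a gap of 56 days it is 56/46/25/4 and 56/39/11. With no gap it is zero.

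**Step 3: two examples.**
- Last dose Day 29, discontinued Day 85. The estimand closes on 29 + 100 = Day 129. Visits fall on 85 + 30/60/100 = Days 115, 145 and 185. A related Grade 3 event with onset on Day 140 and seen at the Day 145 visit is inside 24 weeks and excluded. One with onset by Day 129 is kept, even if found on Day 145.
- Arm D, last dose Day 22, discontinued Day 43. The estimand closes on Day 122, and the last follow-up visit is on Day 143. Of 46 truncated days, 21 come from the mismatch. The other 168 − 143 = 25 lie beyond either window.

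For gaps up to 56 days the Day 30 visit always falls inside the estimand window (56 + 30 = 86 days after last dose). The Day 60 visit falls after the close only if the gap exceeds 40 days. With no gap, only a visit held late in its 7-day allowance falls after it.

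**Step 4: size, on assumed rates.** The documents do not give the inputs. Suppose 10-20% of an arm stop early with no qualifying event, and 2-5% of those later have one in the truncated days. Then 0.10 × 0.02 = 0.2 points and 0.20 × 0.05 = 1 point, or 0.12 to 0.6 participants in 60. This covers the whole truncation in Step 1, so the part due to the mismatch is no larger.

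**Step 5: when it would matter for the comparison.** Take 55% in Arm D as an illustration (the Grade 3-4 rate in Table 5.4.7.1-1) against 38.7%: power with 60 per arm is 69.8%. Losing 1 point in Arm D alone gives 65.8%. Equal losses of 2 points leave it at about 70%. Only an unequal loss affects the comparison.

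**The case against.** The cut is deliberate and stated openly, and last dose is an objective date, whereas a discontinuation date in an open-label trial depends on a decision. That is a fair reason to choose last dose. It does not explain why collection and visits use other dates, or why the rule is called treatment policy.

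It can also be said that few events are at risk. Section 5.5.1.3 reports that the vast majority of ipilimumab immune-related events occurred within 12 weeks of first dosing. Events meeting DLT criteria generally force discontinuation, so many who stop for toxicity already count. Overall AE incidence is a separate secondary endpoint with no last-dose cut stated. All of this stands, and it is why the effect is small. It does not remove the mismatch: Section 7.5.3 also requires a hold for many drug-related Grade 2 events, so a hold does not imply an earlier Grade 3-5 event.

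Three stronger readings are tempting and are not supported:
- **That any event found at a late follow-up visit is dropped.** The rule works on when the AE occurred, not when it was found.
- **That the mismatch costs the full 67/46/25/4 or 67/39/11 days.** Those are the total truncation; the mismatch accounts only for the gap.
- **That Arm D loses more events, so the control rate is understated.** Arm D participants who do not complete induction get no maintenance, while Arms C and F may continue nivolumab, so a difference is possible. But that continuation needs Medical Monitor approval, and both drugs stop if attribution is unclear. Arm D completers are dosed again around Day 85 and are not truncated, and the loss after dose 1 is the same in all arms. No stopping rates by arm are given. An excess loss in Arm D would in any case work against the experimental arms.

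**Conclusion.** The inconsistency is real and sits in the primary safety endpoint of both Part 2A and Part 2B. An event is collected but not counted only if all of these hold: last dose before about Day 68; onset more than 100 days after last dose and by Day 168; no earlier related Grade 3-5 event; and EOT or discontinuation later than last dose. How often the last condition holds depends partly on which EOT description a site applies.

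The expected effect is probably less than one participant per 60-person arm. That rests on assumed stopping and late-event rates. This is a low-cost correction that makes the estimand match the data collected. It does not show that the comparison with Arm D is biased.

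**What to change.** 1. Use one start date for AE collection, follow-up visits and the estimand: the later of last dose and date of discontinuation, as Table 2-5 footnote a already does.
2. In Tables 4-4 and 4-5, replace the exclusion sentences for early discontinuation and for subsequent therapy with: all treatment-related Grade 3-5 AEs with onset through Day 168 and within the safety follow-up period so defined are included. Correct the strategy label to match.
3. If the sponsor keeps the last-dose cut as primary, add a sensitivity analysis of all collected treatment-related Grade 3-5 AEs with onset through Day 168.
4. Reconcile the two EOT descriptions. Do not delete the second: in Tables 2-2 and 2-4 it is probably a separate footnote, and it holds the rule for participants who complete treatment.
5. Reconcile Section 9.2.1, which limits AE collection after new anti-neoplastic therapy, with the estimand, which counts events after subsequent therapy.

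The cost is wording in the protocol and SAP and slightly more analysis. No visits are added, because they are already scheduled from the later date. The reported incidence may rise slightly. The change recovers only the gap days, so an early stopper with no gap is still not counted to Week 24, and the text should say so.

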To evaluate the preliminary safety and tolerability of BMS-986249 in combination with nivolumab (Arm C and Arm F) relative to ipilimumab in combination with nivolumab (Arm D) in participants with previously untreated, unresectable or metastatic melanoma	• Incidence of treatment-related Grade 3-5 AEs within 24 weeks
To evaluate the preliminary efficacy of BMS- 986249 in combination with nivolumab (Arm C and Arm F) relative to historic nivolumab monotherapy data in participants with previously untreated, unresectable or metastatic melanoma	ORR as assessed by investigator using RECIST v1.1
Secondary	
To assess the anti-tumor activity of BMS-986249 in combination with nivolumab (Arm C and Arm F) and ipilimumab in combination with nivolumab (Arm D) in participants with previously untreated, unresectable or metastatic melanoma	ORR, DOR, PFS, and TTR as assessed by investigator using RECIST v1.1
To assess the safety and tolerability of BMS- 986249 in combination with nivolumab (Arm C and Arm F), and ipilimumab in combination with nivolumab (Arm D) in participants with previously untreated, unresectable or metastatic melanoma	Incidence of AEs, SAEs, AEs leading to discontinuation, death, and laboratory abnormalities
To characterize the PK of BMS-986249 when administered in combination with nivolumab	 Summary measures of PK parameters of BMS-986249 in combination with nivolumab
To evaluate time to deterioration (TTD) in Quality of Life (QoL) and physical functioning	• TTD as defined by a minimally important decrease from baseline ≥10 points on the EORTC QLQ-C30 global health status/quality of life subscale (items 29 & 30) and Physical Functioning Scale (items 1 to 5)
Exploratory	
To explore the associations between PK of BMS-986249, ipilimumab and nivolumab, safety, efficacy, and clinical biomarkers such as, but not limited to T cell-specific genes	Association measures between BMS986249, ipilimumab, and nivolumab PK levels, select outcomes, and biomarkers of interest
BMS-986249, ipilimumab and nivolumab, safety, efficacy, and clinical biomarkers such as, but not	ipilimumab, and nivolumab PK levels, select

Protocol Amendment No.: 09

Date: 14-Mar-2023 78

Table 4-2: Objectives and Endpoints: The Dose Expansion Phase in Melanoma (Part 2A)

Objectives	Endpoints	
To characterize the immunogenicity of BMS-986249, ipilimumab and nivolumab	Incidence of ADA to ipilimumab, nivolumab, and BMS-986249	

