Treatment policy (all post-baseline tumor assessment regardless of on-treatment status will contribute to BOR determination)

Intercurrent event: initiation of subsequent anti-cancer therapy

While on treatment (all post-baseline tumor assessment up to initiation of subsequent anticancer therapy will contribute to BOR determination)

Protocol Amendment No.: 09

Table 4-4: Primary Estimands Part 2A

Population level summary: ORR, defined as the number of randomized participants who achieve a BOR of confirmed CR or confirmed PR based on investigator assessments (using RECIST 1.1) divided by the number of all response-evaluable participants in each treatment group, with two sided 60% confidence interval

Estimated odd ratio and 60% confidence interval using Cochran Mantel Haenszel methodology adjusting for stratification factors will be computed. Adjusted and unadjusted chi square test will be performed and p-value will be provided. The difference in ORR (adjusted and unadjusted) will also be provided.

Abbreviations: AE = adverse event; BOR = best overall response; CR = complete response; CTCAE = Common Terminology Criteria for Adverse Events; IV = intravenous; ORR = objective response rate; PR = partial response; Q3W = every 3 weeks; Q4W = every 4 weeks; Q8W = every 8 weeks; RECIST= Response Evaluation Criteria in Solid Tumors.

Table 4-5: Primary Estimands Part 2B

Objective	Endpoint
Primary	Primary
To evaluate the preliminary safety and tolerability of BMS 986249 in combination with nivolumab in participants with previously treated HCC, CRPC, and TNBC	Incidence of treatment-related Grade 3-5 AEs within 24 weeks

Main Estimand for the Primary Objective

Treatment: 1200 mg BMS-986249 IV Q8W +480 mg nivolumab IV Q4W

Population: All treated participants in Part 2B

Variable: Treatment Related AE with CTCAE Grade 3 or higher that occurred within 24 weeks from first dose Intercurrent events: early discontinuation of study

Treatment Policy: Patients that discontinue treatment early will have a 100 days post last dose safety follow-up. AEs occurring after this safety follow-up window will not be included in the analysis, even if they occurred within the 24 weeks from first dose.

Intercurrent event: initiation of subsequent anti-cancer therapy

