5.1.2.4 The BMS-986249 Cohort Expansion Combination Therapy (Part 2)

The purpose of the cohort expansions is to gather preliminary efficacy information in specific populations regarding BMS-986249 in combination with nivolumab. In addition, safety, tolerability, PK, and information will be evaluated. Further, patient-reported quality of life, symptoms, and treatment tolerability will be assessed using the EORTC QLQ-C30, EQ-5D-3L, FACIT GP5, and PRO-CTCAE (see Section 9.9).

The BMS-986249 in Combination with Nivolumab Randomized Cohort Expansion in Melanoma (Part 2A) will evaluate the efficacy and safety of BMS-986249 in combination with nivolumab relative to ipilimumab combined with nivolumab, and historical nivolumab monotherapy data, in a cohort of participants with previously untreated, unresectable or metastatic melanoma. See Section 5.1 and Figure 5.1-2.

The BMS-986249 in Combination with Nivolumab Additional Tumor Cohort Expansion (Part 2B) will evaluate the safety and tolerability of BMS-986249 in combination with nivolumab through single-arm expansion cohorts in previously treated advanced or intermediate HCC, metastatic CRPC, and unresectable locally advanced or metastatic TNBC.

Preliminary reviews of the data in Part 1 and Part 2 will occur prior to the final data base lock, in order to assess the initial safety, PK, and signal. The earliest assessment of the efficacy signal for a Part 2A arm and/or Part 2B tumor cohort may be performed after approximately 15 to 20 participants are randomized into the arm/cohort and complete the first tumor scan (at about 8 to 12 weeks after start of treatment). The evaluation of this preliminary data will assist in further planning for the study, including the option to discontinue treatment arm(s) or de-escalate individual Part 2 arm/cohort dose levels, if supported by the data. The study is expected to continue as planned during this evaluation, until the interpretation of the data is complete. Any changes to the design based on such evaluation may be implemented via a protocol amendment, unless already anticipated and planned for by the current protocol.

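### Does the unnamed contrast in the ORR row of Table 4-4 leave the Part 2A primary efficacy analysis undefined?

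*Combined protocol and SAP*

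**What the plan says.** The primary efficacy objective in Table 4-4 is "To evaluate the preliminary efficacy of BMS-986249 in combination with nivolumab (Arm C and Arm F) relative to historic nivolumab monotherapy data". The Treatment attribute of that row lists Arms C, D and F and no historical reference. The population-level summary has two parts. The first is a response rate per arm: confirmed responders "divided by the number of all response-evaluable participants in each treatment group, with two sided 60% confidence interval". The second is a set of between-group statistics: "Estimated odd ratio and 60% confidence interval using Cochran Mantel Haenszel methodology adjusting for stratification factors will be computed", then adjusted and unadjusted chi-square tests, and finally "The difference in ORR (adjusted and unadjusted) will also be provided". None of these names a contrast. The safety row of the same table does, with "comparison of Arm C vs Arm D and Arm F vs Arm D with estimated difference and odd ratio and 80% confidence interval".

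Other sections bear on the reading:

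- Section 10.1.2.2 says that, with Arm E closed, the efficacy evaluation and comparison use a reference value from historical nivolumab data. The value is redacted.
- Section 5.1.2.4 says Part 2A "will evaluate the efficacy and safety of BMS-986249 in combination with nivolumab relative to ipilimumab combined with nivolumab, and historical nivolumab monotherapy data".
- The secondary objective in Table 4-2, which includes ORR, is "To assess the anti-tumor activity of BMS-986249 in combination with nivolumab (Arm C and Arm F) and ipilimumab in combination with nivolumab (Arm D").
- Section 10.3.1 limits Arms A, B and E to descriptive measures.
- Table 10.3.1-1 gives a chi-square test for Part 2A ORR, with a Cochran-Mantel-Haenszel (CMH) test as sensitivity analysis, again without a contrast. Its footnote sets a two-sided 60% interval for efficacy.

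**The concern.** A primary estimand should say what is compared with what. Here the objective is against a historical figure, while most of the listed statistics are between-group measures that the safety row uses for Arm D. A fixed reference has no rows to enter in a stratified table. The odds ratio and the adjusted test and difference therefore seem to belong to a comparison with Arm D, sitting unlabelled under a different primary objective.

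The unadjusted chi-square and difference are also ambiguous. If they are against the reference, the CMH test called a sensitivity analysis addresses another hypothesis. If they are against Arm D, only the by-arm interval speaks to the primary objective. At stake is misreading: one row could carry a favourable result against the reference and an odds ratio below 1 against Arm D, and a reader might take either as the primary answer.

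**Working it through.** There is no legible ORR power figure to reproduce. The current Part 2A power statement (about 70% with 60 per arm, one-sided 0.10) concerns the safety endpoint, and its rates are redacted. The check is therefore which contrasts are possible, and what follows if they disagree.

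**Which contrast the stratified statistics can take**

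- *Reference value alone.* A CMH calculation with no comparator counts in any stratum returns an undefined odds ratio.
- *Arms A, B, E.* Excluded as comparators by Section 10.3.1.
- *Arm C vs Arm F.* Computable, but no objective names it.
- *Historical strata.* Section 5.4.7.2 gives nivolumab responses by PD-L1 (41/117 below 1%, 94/171 at 1% or above), so an odds ratio stratified on PD-L1 alone could be formed. The plan stratifies on PD-L1 and M-stage, gives no historical M-stage split, and speaks of one reference value.
- *Arm D.* In the Treatment attribute, in the design text, in the secondary objective, and named for the same statistics in the safety row.

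Arm D is the likeliest reading, though it is an inference. A sensitivity analysis normally repeats the main comparison with a different adjustment, so the chi-square paired with CMH in Table 10.3.1-1 is most naturally against Arm D too. The by-arm interval then serves the primary objective.

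**What the two comparisons would show**

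Assumptions: 60 per arm; reference 40% to 45% (the nivolumab rates in Section 5.4.7.2); Arm D at 35/60 = 58.3% (Section 5.4.7.1 cites 58%); Clopper-Pearson by-arm intervals, because the plan names no method; crude odds ratio and Wald difference in place of CMH, because no stratum data exist; z = 0.842 for a two-sided 60% interval.

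For 31/60 = 51.7%:

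- By-arm interval: 45.4% to 57.9%, above either reference.
- Odds ratio vs Arm D: (31 × 25)/(29 × 35) = 0.76. SE of the log = √(1/31 + 1/29 + 1/25 + 1/35) = 0.368, giving 0.56 to 1.04.
- Difference vs Arm D: 0.517 − 0.583 = −0.067. SE = √(0.517 × 0.483/60 + 0.583 × 0.417/60) = 0.0906, giving −14.3 to +1.0 points.

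Other counts:

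| Responders | By-arm 60% CI | OR vs Arm D (60% CI) |
|---|---|---|
| 28/60 | 40.5% to 52.9% | 0.63 (0.46 to 0.85) |
| 30/60 | 43.8% to 56.2% | 0.71 (0.52 to 0.97) |
| 31/60 | 45.4% to 57.9% | 0.76 (0.56 to 1.04) |
| 34/60 | not needed | 0.93 (0.68 to 1.28) |

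The first count to clear a 40% reference is 28, and 31 for 45%. Clearing the reference with an odds ratio below 1 happens at 28 to 34 responders (40%) or 31 to 34 (45%). The whole odds-ratio interval lies below 1 only at 28 to 30, and so only with the 40% reference.

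**Does the open choice for the unadjusted test alter the primary answer?**

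A one-sample statistic, z = (p − p0)/√(p0(1 − p0)/60), can be set against 0.842, the limit that matches a 60% interval:

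- p0 = 0.40: 27/60 gives 0.050/0.0632 = 0.79 (by-arm lower limit 38.9%); 28/60 gives 0.0667/0.0632 = 1.05 (40.5%).
- p0 = 0.45: 30/60 gives 0.050/0.0642 = 0.78 (43.8%); 31/60 gives 0.0667/0.0642 = 1.04 (45.4%).

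Test and interval change over at the same count for both references. Whichever way an analyst reads the unadjusted test, the conclusion against the reference is the same.

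**The case for a change.** The strongest argument for a change is that Table 4-4 is where the plan defines its primary estimands, and the safety row shows that its authors knew how to name a contrast. Redaction hides the reference value but does not explain unredacted sentences that name no comparator in Table 4-4 and Table 10.3.1-1. The likely origin is visible: the 60% interval was set in Section 10.1.2.1 for a difference against concurrent Arm E, and Section 10.1.2.2 replaced that control with a fixed value. The exploratory design explains the lack of multiplicity adjustment but not an unnamed comparator for a primary endpoint.

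The description stands: the label is missing, and naming Arm D as the comparator is an inference. What does not follow is that the analysis is undefined or misdirected. The by-arm interval answers the primary objective, and Section 10.1.2.2 supplies its comparator. An explicit link between the two may exist where text is lost: the reference value is blank, a figure in Section 10.1.2.2 is not shown, and the interval sentence in Section 10.1.2.1 is broken. Section 10.3 also defers detail to a Statistical Analysis Plan to be signed before database lock. Its absence from the visible text cannot be held against the plan.

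**Conclusion.** No change is needed. This is a missing label that a statistician working from the plan would fill sensibly: the by-arm 60% interval for Arms C and F against the Section 10.1.2.2 reference for the primary objective, and the stratified statistics as C vs D and F vs D, in line with the secondary objective and the design text. Both sets of results would be reported under any reasonable reading. No visible success rule rests on the odds ratio or chi-square, and no estimate, sample size or power figure alters.

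The possible disagreement is limited. With Arm D at 35/60, it goes beyond point estimates only at 28 to 30 responders out of 60, and only if the reference is 40%. Even then, an arm better than nivolumab alone but below ipilimumab plus nivolumab is a coherent finding from two different controls. This rests on an assumed reference, an assumed Arm D result and crude rather than stratified statistics. The conclusion that nothing is lost does not depend on those assumptions.
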